REAL-TIME HEAD POSITION STABILIZATION OF HEALTHY VOLUNTEERS

Principal Investigator	[name] Department of Radiation Oncology University of Pennsylvania [name] [name] [contact] [contact]
Funding Sponsor	National Institutes of Health
Study Product	Not applicable
IRB Number	843058
NIH Grant Number	R01-CA227124-02
Version	May 18, 2020 December 14, 2022

CONFIDENTIAL

This material is the property of the University of Pennsylvania.

Table of Contents

BACKGROUND AND STUDY RATIONALE.....	5
1 INTRODUCTION	5
1.1 BACKGROUND AND RELEVANT LITERATURE	5
2 STUDY OBJECTIVES	5
2.1 PRIMARY OBJECTIVE.....	5
3 INVESTIGATIONAL PLAN.....	5
3.1 GENERAL DESIGN	5
3.2 STUDY ENDPOINTS.....	6
3.2.1 Primary Study Endpoint	6
4 STUDY POPULATION AND DURATION OF PARTICIPATION	6
4.1 DURATION OF STUDY PARTICIPATION.....	6
4.2 TOTAL NUMBER OF SUBJECTS AND SITES.....	6
4.3 INCLUSION CRITERIA	6
4.4 EXCLUSION CRITERIA.....	6
4.5 SUBJECT RECRUITMENT.....	6
4.6 VULNERABLE POPULATIONS	6
5 STUDY PROCEDURES.....	7
5.1 SCREENING	7
5.2 STUDY INTERVENTION	7
5.3 SUBJECT WITHDRAWAL	7
5.3.1 Data Collection and Follow-up for Withdrawn Subjects	7
6 STATISTICAL PLAN	7
6.1 SAMPLE SIZE AND POWER DETERMINATION.....	8
7 SAFETY AND ADVERSE EVENTS.....	8
7.1.1 Data and Safety Monitoring Plan	8
8 STUDY ADMINISTRATION, DATA HANDLING AND RECORD KEEPING	8
8.1 CONFIDENTIALITY	8
8.2 DATA COLLECTION AND MANAGEMENT	8
9 STUDY MONITORING, AUDITING, AND INSPECTING	8
9.1 STUDY MONITORING PLAN.....	8
9.2 RISKS AND BENEFITS	8
9.3 INFORMED CONSENT PROCESS / HIPAA AUTHORIZATION	8
10 STUDY FINANCES	9
10.1 FUNDING SOURCE.....	9
10.2 CONFLICT OF INTEREST.....	9
10.3 SUBJECT STIPENDS OR PAYMENTS	9
11 PUBLICATION PLAN	9

CONFIDENTIAL

Study Summary

Title	Real-Time Head Stabilization of Healthy Volunteers
Short Title	Head Stabilization- Volunteers
IRB Number	843058
Protocol Number	Not applicable
Methodology	Observational
Study Duration	24 months
Study Center(s)	Single-center
Objectives	
Development of an advanced motion control system.Design and construction of a clinical robotic stereotactic radiosurgery system (SRS) using real-time 3D image tracking.Validation of the SRS.
Number of Subjects	20 subjects
Main Inclusion and Exclusion Criteria	Healthy individuals will be recruited to this study.
Intervention	Head motion data collection using motion-detection cameras.
Statistical Methodology	The endpoint is purely quantitative in nature and will be determined by analyzing the real-time 6D target motion during the SRS procedure.

CONFIDENTIAL

This material is the property of the University of Pennsylvania.

Data and Safety Monitoring Plan	The Principal Investigator will be responsible for the data quality management and the ongoing safety of subjects.
--	---

CONFIDENTIAL

This material is the property of the University of Pennsylvania.

Background and Study Rationale

This study will be conducted in full accordance with all applicable University of Pennsylvania Research Policies and Procedures and all applicable Federal and state laws and regulations including as applicable include the following regulations as they apply 45 CFR 46, 21 CFR Parts 50, 54, 56 All episodes of noncompliance will be documented.

1 Introduction

This is a single-center observational study in which we aim to collect real-time head motion in healthy volunteers. This data is a first step in developing an advanced motion control system for head stabilization in patients undergoing whole brain radiation therapy.

1.1 ***Background and Relevant Literature***

Stereotactic radiosurgery (SRS) is a therapy modality used for the treatment of brain disorders with precise radiation dose placement[1], [2]. To achieve the 1-2 mm precision for intracranial SRS, a metal head ring is rigidly fixated to the patient's skull using screws under local anesthesia, and then bolted on the treatment couch [3]. The discomfort, inconvenience, and invasive nature associated with the frame preparation have been identified as the main cause of poor patient compliance and poor clinical efficiencies when SRS is medically indicated[4]. For certain patients, with extreme cranial anatomy or prior surgical bone flaps, ring placement is not possible. In addition, the frame prohibits cases when a hypo-fractionated schedule is desired leading to the use of techniques with far less accuracy. For clinics, with tight patient LINAC scheduling, or high patient to LINAC volumes, frame based SRS scheduling can prove to be problematic due to the necessity of performing the CT scan, planning, setup, and treatment on the same day. Recent research, aimed at eliminating the ring placement, has so far resulted in implementations of frameless SRS with less accuracy than frame based SRS[5], [6]. Removal of the head ring allows room for small intrinsic head motions to occur. No radiotherapy delivery device has yet been developed to correct for such deviations.

2 Study Objectives

The goal of our research is to develop a next generation frameless SRS approach where such small intrinsic head motions are continuously cancelled/corrected throughout SRS treatment. Similar to a noise cancellation headset, where outside noise is sampled, shifted in phase by 180°, and then added to the incoming sound for cancellation, the proposed method will sample head motion using real-time 6D optical tracking, calculate its inverse, and add it to incoming head motion using a robotic 6DOF head stage for cancellation of patient head motion. This approach has the potential to be less invasive than current frameless SRS techniques while still achieving accuracies better or equal to traditional frame based SRS.

2.1 ***Primary Objective***

This particular study aims to passively monitor the real-time head motions of healthy volunteers positioned to simulate whole brain radiation therapy. Such real-time head motion data is necessary in order to understand the type (amplitude/frequency) of motion that the robotic stage will be expected to compensate for and will play an important role in the overall modeling and designing process of the robotic prototype.

3 Investigational Plan

3.1 ***General Design***

CONFIDENTIAL

The study will consist of cancelling the head motions of 20 volunteers lying in a comfortable supine position. The volunteer population will consist of healthy individuals including individuals associated with The University of Pennsylvania.

The real-time head monitoring will be performed using either an optical camera 3D surface imager (AlignRT, VisionRT, UK) or IR marker camera (Polaris, NDI, Canada) that is either mounted to the ceiling or supported on a tripod. Both cameras are FDA approved medical devices that are routinely used in our clinic. Similar to a video camera, real-time head position monitoring by the camera will be performed passively and will not interfere with the volunteer. Using the real-time head position data provided by the camera, a motion stage placed under the head support will slowly move in order to cancel out small motions in order to maintain a stationary head position.

3.2 *Study Endpoints*

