5.2 Study Intervention

The AlignRT system consists of three units attached to the ceiling where one unit is located at each lateral side of the patient treatment table and one at the center above the foot of the table. Each unit contains two cameras, which take pictures at slightly different perspectives, allowing for image depth reconstruction (3D surface image). Analysis and comparison of these 3D surface images as taken during the course of treatment can allow extraction of patient motions during treatment.

The Polaris infrared (IR) camera consists of a single unit either attached to the ceiling or mounted on a tripod. Each unit contains two cameras, which take pictures of IR markers attached to the volunteers head at slightly different perspectives, allowing for triangulation of the marker positions and thus determination of head position.

As both the AlignRT and Polaris devices use optical camera monitoring, it is non-invasive and will not physically touch or interfere with the volunteer. Both systems are routinely used in the clinic for assuring that patients are correctly positioned on the treatment table. The research proposed here does not deviate from the FDA approved operation of the AlignRT or Polaris in anyway.

The volunteer head support (Freedom Pursuit Robotic Platform, CDR Systems, Canada) consists of a stage that can both move and rotate along the volunteers superior-inferior (SI), anterior-posterior (AP), and left-right (LR) directions using electric motors. The motions produced by the stage are in the millimeter range.

The volunteer will be requested to lie down in a relaxed supine position with their head supported on top of the stage. The AlignRT or Polaris camera system will be initialized and made to track the real-time motions of the volunteer's head. Real-time head motion tracking will proceed for approximately 15 – 30 minutes with either the motion compensation stage turned on or off. All volunteer head motion will be logged for later analysis.

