5.3.1 Data Collection and Follow-up for Withdrawn Subjects

Subjects undergo a one-time head motion detection session, there is no follow-up once the session is completed or once subjects withdraw.

6 Statistical Plan

The data collected will not be reviewed until the study is closed to accrual. Volunteer head motion data, acquired in Sec. 5, will then be imported into Matlab research software and analyzed in terms of quantifying several basic motion parameters such as mean and maximum positional deviation, velocity of

CONFIDENTIAL

the motion, and net motion trajectory. These results will be used to quantify the performance of the head positioning stage in maintaining an accurate head position.

6.1 *Sample Size and Power Determination*

This is a pilot study to collect baseline data, sample size and power calculation is not necessary.

7 Safety and Adverse Events

The head motion detection sessions are non-invasive and do not involve any procedures that would pose risk to any subject nor result in any adverse events. Adverse events are not applicable to this study and will not be tracked.

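### The camera that steers the stage is the only described source of the log that judges it, so the stage-on log shows camera-seen residual motion, not accuracy of head position

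*Combined protocol and SAP*

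**What the plan says.** All references are to the combined protocol and SAP.

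- **Measurement (Section 3.1, General Design).** "The real-time head monitoring will be performed using either an optical camera 3D surface imager" or an infrared marker camera. Section 5.2 repeats the either/or: "The AlignRT or Polaris camera system will be initialized and made to track the real-time motions".
- **Control (Section 3.1).** The camera's output drives the stage: "Using the real-time head position data provided by the camera, a motion stage placed under the head support will slowly move".
- **Session (Section 5.2).** Tracking lasts about 15 to 30 minutes, "with either the motion compensation stage turned on or off", and the head motion is logged.
- **Analysis (Section 6).** The log from Section 5 is to be "analyzed in terms of quantifying several basic motion parameters such as mean and maximum positional deviation". Net trajectory and velocity are listed as well.
- **Conclusion drawn (Section 6).** "These results will be used to quantify the performance of the head positioning stage in maintaining an accurate head position".

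No tracker outside the control loop, phantom run, or figure for camera error or drift is described, though none is ruled out. Section 3.2.1 makes data collection the primary endpoint. Section 6.1 calls the study a pilot and gives no sample size calculation. No accuracy threshold or decision rule is set.

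**The concern.** A feedback loop drives its own input towards zero. If the log used to judge the stage is that same input, a small logged deviation shows that the stage obeyed the camera. It does not show that the head was where it should have been. When the camera reading drifts slowly, the stage moves the head to keep the reading constant. The log stays flat while the head is carried off.

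One Section 6 conclusion is at stake, the performance statement about accuracy. The stage could look more accurate than it is, and more volunteers would not reveal this. For context, Section 1.1 gives a scale for the wider programme: "To achieve the 1-2 mm precision for intracranial SRS".

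**Working it through.** The plan states no figure to reproduce, so the check is of the mechanism and of its possible size.

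**Inputs from the documents.** Session of 15 to 30 min (Section 5.2); one camera, AlignRT or Polaris, as position source (Sections 3.1 and 5.2).

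**Assumptions, not in the documents.** One axis; an integrating control loop with time constant τ of 2, 20 or 200 s; head motion SD 0.5 mm with 60 s exponential correlation; log at 10 Hz; session T = 20 min = 1200 s; linear camera drift reaching D mm at the end.

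**Model.** Log m = x + e, where x is true head position and e is camera error. The stage moves at rate −m/τ. Error that is slow relative to τ leaves m almost unchanged and gives x ≈ −e.

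**Closed form when the drift is fully followed.**

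- Logged RMS = √[0.25·τ/(τ+60)], which does not contain D.
- True RMS = √[0.25·τ/(τ+60) + D²/3].

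For τ = 2 s:

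- Logged: √(0.25 × 2/62) = √0.00806 = 0.09 mm.
- True, D = 0.5: √(0.00806 + 0.0833) = 0.30 mm.
- True, D = 0.1: √(0.00806 + 0.0033) = 0.11 mm.

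For τ = 20 s:

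- Logged: √(0.25 × 20/80) = √0.0625 = 0.25 mm.
- True, D = 0.5: √(0.0625 + 0.0833) = 0.38 mm.
- True, D = 0.1: √(0.0625 + 0.0033) = 0.26 mm.

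For τ = 200 s the stage no longer follows the drift fully. The lag left in the log approaches (D/T)·τ = (0.5/1200) × 200 = 0.083 mm, so the formula above overstates the gap and simulation is used instead.

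| Drift 0.5 mm over 20 min | True RMS (mm) | Logged RMS (mm) |
|---|---|---|
| 2 s loop | 0.30 | 0.09 |
| 20 s loop | 0.38 | 0.25 |
| 200 s loop (simulated) | 0.50 | 0.45 |

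Simulation agrees with the closed form for the first two rows. The gap shrinks as the stage follows less.

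**Sensitivity, D = 0.5 mm.**

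- Head motion SD 0.2 mm: 0.29 against 0.04 mm (2 s), 0.30 against 0.10 mm (20 s).
- Head motion SD 1.0 mm: 0.34 against 0.18 mm (2 s), 0.57 against 0.50 mm (20 s).
- Sessions of 15 or 30 min change RMS by less than 0.01 mm.

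**Separate check with a still head.** With loop gain K = 0.2 per s and 1 mm drift over 1800 s, the log settles at (1/1800)/0.2 = 0.0028 mm while the head ends 0.997 mm off. For K from 0.02 to 1 per s, the log maximum is 0.028 to 0.0006 mm and the true displacement 0.97 to 1.00 mm.

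**Where the effect stops.** Error too fast for the stage does appear in the log. At K = 0.2 per s, a 1 mm sinusoidal camera error gives a logged maximum of about 1.0 mm at a 5 s period, 0.25 mm at 120 s and 0.05 mm at 600 s.

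**Abrupt marker slip of 0.5 mm at mid-session.** It enters the log as a step and decays as 0.5·exp(−t/τ). The logged maximum rises from 0.35 to about 0.51 mm (2 s loop) or from about 0.83 to 0.87 mm (20 s loop). The offset then stays on the head for half the session: true RMS √(0.00806 + 0.25/2) = 0.36 mm against 0.09 logged (2 s), and √(0.0625 + 0.25/2) = 0.43 mm against 0.25 logged (20 s).

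**The case against.** The strongest reply is that no harm has been shown. No camera drift is documented. Sections 3.1 and 5.2 say that both cameras are FDA approved and routinely used for patient positioning. This is a pilot whose endpoint is data collection. All of that stands and keeps the weight low. It supplies no error bound, however, and the stage-on log cannot tell a 0.1 mm drift from a 1.0 mm one when the stage follows it.

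The loop may also be slow, since Section 3.1 describes slow stage movement. With a 20 s loop and a drift of up to 0.2 mm, the RMS gap is only about 0.27 against 0.25 mm. That stands too, and the 2 s figures should not be read as typical.

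The documents do not say outright that the analysed log is the steering camera's own. It is the only position source they describe, so this is the natural reading.

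Four stronger readings are tempting, and the documents do not support them:

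- *The log hides every camera error.* It hides only gradual error that the stage follows. Fast error shows, and an abrupt slip leaves a brief step that could be read as head motion before its lasting offset disappears.
- *The stage is inaccurate.* Nothing in the documents says how large the drift is.
- *An on/off comparison will be inflated.* The plan defines no such comparison, and Section 5.2 does not establish that each volunteer is recorded in both states.
- *The study fails the 1-2 mm standard.* That figure describes ring-fixed radiosurgery. Sections 1 and 2.1 place this study in a whole brain radiation setting, so it is context and not a criterion.

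**Conclusion.** The point holds, with minor weight. Followed exactly, Section 6 yields residual motion as seen by the controlling camera, and its wording claims more than that.

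The direction is certain for slow error under any loop that follows it. The size is not known. Under the stated assumptions it runs from negligible (0.1 mm drift: 0.11 against 0.09 mm, or 0.26 against 0.25 mm) to a true RMS about three times the logged one (0.5 mm drift, 2 s loop: 0.30/0.09 ≈ 3.3), and it is small again for a very slow loop.

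Collection of head-motion data is not affected. Stage-off recordings are free of this feedback effect and carry only ordinary camera error.

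**What to change.** In Section 6:

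1. Limit the performance conclusion to residual motion as seen by the controlling camera, and report results separately for AlignRT and Polaris.
2. Beside it, report each used camera's drift and noise from one static phantom recording of session length, with the stage held still. State that this covers instrument drift only, and not marker slip, skin motion or session-to-session variation.

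One recording is precise enough for this purpose. With assumed linear drift and white noise of SD 0.3 mm at 10 Hz for 20 min (12,000 readings), a straight-line fit gives the drift with standard error 0.3 × √(12/12,000) ≈ 0.009 mm.

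The cost is one bench recording per camera used and a change of wording. The conclusion becomes narrower and possibly less favourable to the stage. No volunteer time is added.

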3.2.1 Primary Study Endpoint

The primary endpoint is collection of head motion data to be used in developing head stabilization methods in brain radiation patients.

4 *Study Population and Duration of Participation*

The volunteer population will consist of healthy individuals. Subjects will be recruited by the PI and his research team. We do not plan to use any internet, radio, newspaper etc. advertisements for this study. Subjects will undergo a one-time motion detection session.

4.1 *Duration of Study Participation*

Subjects will be considered “on study” from consent through completion of the head stabilization session; there is no follow-up involved.

4.2 *Total Number of Subjects and Sites*

This is a single-institution study for which we aim to accrue 20 subjects.

4.3 *Inclusion Criteria*

Inclusion criteria are:

- Subjects 18 and older
- Subjects must be able to read and understand English
- Participants must sign the informed consent form

4.4 *Exclusion Criteria*

Any subjects not meeting the above inclusion criteria will not be considered for this study.

4.5 *Subject Recruitment*

Subjects will be recruited from staff, faculty, and students of the University of Pennsylvania.

4.6 *Vulnerable Populations*

Children, pregnant women, fetuses, neonates, or prisoners are not included in this research study.

CONFIDENTIAL

This material is the property of the University of Pennsylvania.

5 Study Procedures

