7.1.1 Data and Safety Monitoring Plan

The Principal Investigator will monitor the study for data integrity and subject safety. As this study involves non-invasive methods to measure head motion, we determine this study to be of minimal risk to participants.

8 Study Administration, Data Handling and Record Keeping

8.1 *Confidentiality*

All research personnel will be trained to maintain confidentiality and never to discuss study participants or individual research data publicly or in any private setting where they could be overheard.

Name and date of birth will be collected from subjects only to confirm eligibility. All data collected during the head motion detection session will be identified only by subject number. We will not be collecting any PHI.

8.2 *Data Collection and Management*

All research files and computer databases will be stored in secure locations within the University of Pennsylvania's Department of Radiation Oncology, with access limited to members of the research team. These data files will be maintained for five years after the study is completed and then destroyed and/or erased. Data will not be shared with the study sponsor. Individual data will be reported only in the aggregate.

9 Study Monitoring, Auditing, and Inspecting

9.1 *Study Monitoring Plan*

The study PI will be responsible for ensuring the ongoing quality and integrity of the research study.

9.2 *Risks and Benefits*

There are no risks to volunteers as the optical camera tracking process is passive and the type of motions generated by the motion stage are on the order of millimeters. The data generated by this research study are not expected to benefit the subjects personally. The primary benefit of participation in this study would be to contribute to the development of improved SRS methods. The experimental data do not have any clinical use and will be used only for research purposes.

9.3 *Informed Consent Process / HIPAA Authorization*

All subjects for this study will be provided a consent form describing this study providing sufficient information for subjects to make an informed decision about their participation in this study. This consent form will be submitted with the protocol for review and approval by the IRB for the study. Potential subjects will review the consent form in detail with the person designated to consent (either PI or CRC) and have the ability to take the consent home for further review. We request waiver of documentation of

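### Do the entry, recruitment and consent statements conflict enough to require a change to the protocol?

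*Combined protocol and SAP*

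**What the plan says.** Entry is governed by several parts of the combined protocol and SAP.

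- **Listed criteria (4.3, 4.4).** A participant must be an adult, be able to read and understand English, and give signed consent: "Participants must sign the informed consent form". Section 4.4 has no separate exclusions: "Any subjects not meeting the above inclusion criteria will not be considered for this study".
- **Health.** The Summary row on main inclusion and exclusion criteria says "Healthy individuals will be recruited to this study". The title, 2.1, 3.1 and the opening of Section 4 also limit the study to healthy people. The term is not defined.
- **Pregnancy and other groups (4.6).** "Children, pregnant women, fetuses, neonates, or prisoners are not included in this research study".
- **Source of volunteers.** Section 3.1: "The volunteer population will consist of healthy individuals including individuals associated with The University of Pennsylvania". Section 4.5: "Subjects will be recruited from staff, faculty, and students of the University of Pennsylvania".
- **Checking eligibility.** Section 5.1 describes a face-to-face consent discussion, after which a person found eligible is scheduled. Section 8.1 adds: "Name and date of birth will be collected from subjects only to confirm eligibility". Section 9.3 states that no health information is gathered.
- **Consent record (9.3).** The protocol asks for documentation of consent to be waived on grounds of minimal risk. It does not say whether the request was granted.

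**The concern.** A reader who treats 4.3 and 4.4 as the complete entry rule meets three difficulties.

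First, a pregnant or unwell adult who reads English and signs the form passes every listed criterion, although other sections say such a person is not included. The items collected for eligibility, name and date of birth, can support the age criterion but not these limits, so the records described could not later show that the sample was healthy.

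Second, a healthy adult from outside the university fits 3.1 and 4.3 but is not in the groups that 4.5 names. Whether that person counts toward the 20 seems to depend on the section consulted.

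Third, one section makes a signature a condition of entry while another asks to dispense with it. If the waiver were granted and used, every unsigned participant would fail a written criterion. The Background section says "All episodes of noncompliance will be documented", which seems to turn each such enrolment into a reportable event.

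At stake would be the definition of the evaluable sample and the audit trail behind the word healthy.

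**Working it through.** The plan gives no figure to reproduce: 6.1 states that no sample size or power calculation is needed. The check is therefore a comparison of the statements.

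**1. Recruitment source, 3.1 against 4.5.** Section 3.1 describes a population, healthy people including those with a university connection. Section 4.5 says where the team will look: staff, faculty and students. The second group is a subset of the first. Recruiting from a subset does not contradict a broader description, and 4.5 does not say that nobody else may enter. Section 5.1 names the same three groups when it deals with undue pressure, which supports reading 4.5 as the practical source. Section 5.1 also allows word of mouth, so an outside adult is not expressly barred. That leaves a small ambiguity, not a contradiction.

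**2. Health and pregnancy, 4.3 and 4.4 against the Summary, Section 4 and 4.6.** The limits are missing from the numbered list but not from the protocol. The Summary states the health limit under its heading for inclusion and exclusion criteria, Section 4 repeats it, and 4.6 comes two headings after 4.4. The age criterion already covers children, fetuses and neonates. That leaves health, pregnancy and prisoner status as limits stated outside the list. A team working from the whole protocol would enrol healthy, non-pregnant adults.

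**3. Records of eligibility, 8.1.** Two items are collected, name and date of birth. Neither bears on health or pregnancy, so those limits can be confirmed from the described records for 0 of 20 subjects. The same count gives 0 of 20 for English, which is a listed criterion, yet the consent discussion in 5.1 plainly can establish it. The figure therefore says only that no record is described; it does not show that no check is made. In 8.1 the word *only* restricts the purpose for which name and birth date are used. It does not make them the sole means of judging eligibility, and a spoken question remains open to the team.

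**4. Signature, 4.3 and 4.4 against 9.3.** There are two bounds:

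- all participants sign: 0 of 20 depart from 4.3;
- waiver granted and no signatures taken: 20 of 20 depart from 4.3 as written.

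The conflict in the text is real. In practice it depends on the outcome of the request, and a waiver permits unsigned consent without forbidding signatures.

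**5. The sentence on noncompliance.** It closes a paragraph on university policy and on federal and state regulation, and it does not mention entry criteria. If the waiver were granted, that sentence would not by itself establish 20 episodes of noncompliance.

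**6. Effect on the analysis.** Section 6 plans descriptive summaries of mean and maximum positional deviation, velocity and net trajectory. None uses the form of consent or the recruitment channel as an input. No error rate, margin or power figure is stated that could move.

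**The case for a change.** The strongest case for acting is the consent point. Reading the sections together cannot reconcile a criterion that requires a signature with a request to do without one. If the waiver is granted and used, the criterion is breached; if everyone signs, the request serves no purpose. The repair would be a few words, and an operative criteria list should not omit a limit that the Summary presents as a main criterion. The word healthy is in the title, is never defined, and has no described record behind it.

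Much of this stands as description. Sections 4.3 and 9.3 do not agree, no health record is described, and the list in 4.3 is shorter than the set of limits the protocol states. What does not stand is the step from there to a needed change. The mismatch affects how consent is documented, not who is measured or how. The health and pregnancy limits already bind the team where they are written, so moving them is a matter of placement. Recording a health confirmation would also have a cost: the statement in 9.3 that no health information is gathered would have to be edited, and the HIPAA position there and the statement in 8.1 on PHI would need to be checked again. For a one-session pilot that the protocol classes as minimal risk, no analytic return is shown for that work.

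**Conclusion.** No change to the plan follows. One genuine inconsistency remains, between the signature criterion in 4.3 (enforced by 4.4) and the waiver request in 9.3. It is a clerical slip that takes effect only if the waiver is granted and used, and it could be tidied whenever the protocol is next edited. The recruitment statements are compatible, and the health and pregnancy limits are stated, though outside the numbered list.

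The effect on any planned result is nil on the documents: no motion summary, precision figure or sample size rationale depends on these statements. The counts of 0 of 20 and 20 of 20 express an absent record and an unknown decision; they do not measure harm.

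This rests on two assumptions. The study team applies the Summary, Section 4 and 4.6 together with 4.3, as any team working from the full protocol would. And the consent procedure used is the one the IRB approved, whichever way it ruled on the waiver. Evidence that people outside the stated limits had been enrolled would reopen the question, but nothing in the documents suggests it.
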